Participant	An individual who takes part in a study
PO	Project Office
REC	Research Ethics Committee
REDCap	Research Electronic Data Capture
S-CIUS	Short-Compulsive Internet Use Scale
SAB	Scientific Advisory Board
SC	Steering Committee
SDQ	Strengths and Difficulties Questionnaire
SERI	Swiss State Secretariat for Education Research and Innovation
SRHI	Self-Report Habit Index
SOCS	Short Obsessive Compulsive Disorder Screener
SOP	Standard Operating Procedure
SST	Stop-Signal-Task
TSC	Trial Steering Committee
UK	United Kingdom
UKRI	Research and Innovation Fund, Innovate UK program
UPPS-P	Urgency – Premeditation - Perseverance - Sensation Seeking - Positive Urgency
WP	Work Package
WHODAS 2.0	World Health Organisation Disability Assessment Schedule

Study Summary

Full title	Boosting Societal Adaption and Mental Health in a Rapidly Digitalizing, Post-Pandemic Europe
Short title/Acronym	BootStRaP
Protocol Number and Date	Version 2.0 01/10/2025
Start Date	When approvals have been received (REC)
End Date	01/09/2028
Study Duration	Cohort 2: 12 months + 28-month extension Cohort 3: 12 months
Study Design	A controlled, individual randomised, observer-blinded, three-arm pilot trial followed by a definitive randomised control trial (RCT)
Sponsor/Co-sponsors	The University of Hertfordshire
Chief Investigator(s)	[name]
Funder	European Union, European Health and Digital Executive Agency (HADEA), Research and Innovation Fund, Innovate UK program (UKRI), Swiss Confederation, State Secretariat for Education Research and Innovation (SERI)
Study Objective(s)	
The aim of this phase of the study, which incorporates both a pilot study (cohort 2) and an RCT (cohort 3), is to investigate two promising theory-informed candidate preventative interventions, targeting A: emotional regulation and B: inhibitory control, for Problematic Use of the Internet (PUI).
 
For the Pilot study: The primary objective is to use participants' individual characteristics to build models for predicting that predict outcomes for both novel preventative interventions when compared to a control condition (non-interactive provision of information on PUI).
 
The secondary objective is to explore the effectiveness of each preventative intervention compared to a control condition when allocated at random.
 
For the RCT: The primary objective is to evaluate the effectiveness of the predictive models derived from the pilot. We achieve this by comparing the effectiveness of each intervention (i.e., targeting emotional regulation or inhibitory control) when allocated either according to an algorithm derived from individual baseline outcome predictors (tailored arm), or when allocated at random (random arm) versus a control condition (non-interactive provision of information on PUI).
 
The secondary objective is to evaluate and compare the cost-effectiveness and cost utility of both allocation methods (tailored, random), investigating feasibility for large-scale implementation.

Planned Sample Size	3,600 (approximately 400 young people at each site), per cohort.
Participants	Young adolescents aged 12-16

Intervention	
Two 4-week digital self-help preventative interventions have been developed based on two different theoretical underpinnings (emotional regulation and inhibitory control).
 
Pilot study: Participants will be randomly allocated to one of three interventions (emotional regulation; inhibitory control; control condition). The preventative interventions will be stratified into high and low intensity versions and allocated to individuals according to high and low risk of PUI based on a detailed baseline assessment and mobile sensing data.
 
RCT: Participants will receive similar interventions as in the pilot study but allocated in a different way. Participants will be randomised to three separate arms (tailored; random; control), and all will undergo a detailed baseline assessment. For those allocated to the tailored arm, the presence at baseline assessment of risk factors derived from the pilot study will serve as predictors and be used to allocate participants to the intervention (emotional regulation or inhibitory control) most likely to be effective at preventing PUI or reduce problematic behaviour patterns. For those allocated to the random arm, participants will be allocated at random to either of the emotional regulation or inhibitory control interventions.

Follow up duration	
Pilot study: The primary endpoint is the post intervention assessment that takes place at the end of the 4-week intervention phase. The secondary endpoint takes place at 3-months following the primary endpoint. Additional assessments will take place 3-monthly during an optional additional 24-month extension phase.
 
RCT: The primary endpoint takes place at the post intervention assessment at the end of the 4-week intervention phase. The secondary endpoint takes place at 6-months following the primary end point.

Outcomes	
The primary outcome of both the pilot study and the RCT will be PUI measured using the Problematic Internet Use Questionnaire in its short version (PIUQ-SF-9)(Demetrovics et al., 2008).
 
As a secondary outcome, smartphone behaviour will be monitored using mobile sensing giving insights into variables linked to PUI.

1. Introduction

1.1. Study Background and rationale

Problematic use of the internet (PUI) is a public health concern in an era of digital technology where young people become familiar with computers, mobile devices and the Internet at very early ages. Although young people's internet use has many functional and enriching aspects, some adolescents may develop unhealthy patterns of internet use and may experience associated health issues which develop early in life and once present tend to endure (Brand, 2022; Brand et al., 2019; Gjoneska et al., 2021). Given that the use of Smartphones and the Internet is widespread and plays a significant role in users developing PUI, especially young populations, measures to prevent and reduce the risk of PUI are of special importance (Fineberg et al., 2018).

Research on interventions for Problematic Internet Use (PUI) remains limited (King et al., 2018; Nakayama et al., 2017; Vondráčková & Gabrhelík, 2016) and methodologically weak (King et al., 2011;

King & Delfabbro, 2014; Rumpf et al., 2018, 2019). Nonetheless, reviews highlight promising strategies, including both primary and secondary prevention (King et al., 2018). School-based programs show potential for universal and targeted prevention among adolescents (Throuvala et al., 2019, 2021), though interventions must be accessible across varying risk levels.

Evidence for interventions targeting adolescents with Problematic Usage of the Internet (PUI) remains limited. A review by Throuvala et al., (2019) identified three promising approaches: Cognitive Behavioural Therapy (CBT) (Lindenberg et al., 2017), media literacy (Walther et al., 2014), and interventions aimed at enhancing awareness and protective factors (Bonnaire et al., 2019). However, a systematic review and meta-analysis on primary prevention effectiveness in adolescents found no significant overall effect, despite some positive individual outcomes (Saletti et al., 2021). Similarly, Yeun & Han (Yeun & Han, 2016) reported benefits from school-based psychosocial interventions, though findings were limited to studies conducted in Korea, with only two RCTs included.

Psychological treatments for established internet and smartphone addiction have shown moderate effectiveness (Kim & Noh, 2019; Liu et al., 2017; Malinauskas & Malinauskiene, 2019). Digital interventions, due to their scalability and cost-effectiveness, are increasingly seen as a promising avenue. While evidence supports their use in treating gambling disorder, further research is needed to confirm their efficacy for other internet-related conditions such as gaming and pornography use (Boumparis et al., 2022). Recent studies have shown promising results using Attentional Bias Modification (Nasiry & Noori, 2022) and Emotional Bias Modification in Gaming Disorder (Wu et al., 2022).

CBT-based interventions remain central to treatment, though earlier reviews highlight methodological limitations and a lack of high-quality trials (King et al., 2011; King & Delfabbro, 2014; Stevens et al., 2019; Zajac et al., 2017, 2020). More recent studies (Kaushik et al., 2023; Wölfling et al., 2019) suggest improved outcomes, potentially due to targeting underlying neural mechanisms (Antons et al., 2020).

Crucially, not all participants in preventative or clinic interventional studies of PUI respond equally to specific interventions. Effectiveness is influenced by individual risk factors, additional characteristics and comorbid conditions. For instance, a meta-analysis using machine learning (ML) in CBT research reported an overall predictive accuracy of 74% when integrating clinical, neuroimaging, cognitive, and genetic data, or a combination of these as predictors (Vieira et al., 2022). Researchers recommend leveraging statistical models to enhance interventions specificity in mental health treatment (Cohen & DeRubeis, 2018; Delgadillo & Lutz, 2020). For example, tailored interventions addressing comorbidities have outperformed standard CBT in treating gaming disorder (Torres-Rodríguez et al., 2018).

In summary, while there is growing evidence supporting both preventative and clinical interventions for PUI, high-quality, individualised, and scalable approaches—particularly digital ones—are urgently needed to address this complex and evolving issue.

Based on the reviewed literature, it is evident that the number of high-quality, methodologically rigorous studies remains limited. While systematic reviews and meta-analyses provide some insights, their conclusions are constrained by the small number of available studies and inconsistent findings. According to the Oxford Centre for Evidence-Based Medicine criteria (<http://www.cebm.net/index.aspx?o=5653>),

the current body of evidence falls between levels 2 and 3, highlighting the need for further well-designed research to strengthen the reliability of findings.

The pilot study aims to develop two digital self-help preventative interventions for PUI that will be tested to derive information on tailored interventions based on machine learning (ML). The subsequent RCT aims at testing tailored interventions based on the results of the Pilot Study. The rationale behind this approach is that individuals with PUI will respond differently to the candidate interventions developed in the Pilot Study (emotional regulation intervention: improving emotional regulation and social competence; inhibitory control intervention: improving inhibitory control and cognitive biases). Risk factors and additional characteristics identified in the pilot study will serve as predictors to allocate participants in the RCT to the intervention most likely to prevent PUI or reduce problematic behaviour patterns.

Both the pilot study and RCT follow the assessment study phase of the Bootstrap project, which was the first of the three studies conducted during the whole BootStRaP project. The main aim of the assessment study was to determine the multifactorial determinants of healthy vs. unhealthy internet usage among European adolescents aged 12-16 years and develop algorithms for quantifying individual risk of PUI.

2. Aims and Objectives

2.1. Study objectives

The second phase of the BootStRaP project aims to evaluate two promising, theory-informed preventative interventions for Problematic Usage of the Internet (PUI). This phase consists of a pilot study and a randomised controlled trial (RCT), designed to refine intervention strategies and optimise participant allocation.

Pilot Study

The primary objective of the pilot study is to identify key predictive characteristics that determine individual responses to the two interventions (emotional regulation and inhibitory control), compared to a control condition (non-interactive provision of psychoeducation on safe and effective use of the internet).

The secondary objective is to assess the overall effectiveness of each intervention relative to the control group under random allocation.

We do not expect one intervention to be superior to the other; rather, both are anticipated to be more effective than the control condition in reducing PUI risk. However, the primary focus is not on comparative effectiveness but on developing algorithms for personalised intervention matching, which will be applied in the subsequent RCT.

Randomised Control Trial

The primary objective of the RCT is to determine whether tailored intervention allocation (matching participants to either the emotional regulation intervention or inhibitory control intervention, using machine learning algorithms developed in the pilot study) leads to better outcomes compared to random allocation to the emotional regulation intervention or inhibitory control intervention or the control arm.

The secondary objective is to evaluate the cost-effectiveness and cost utility of this tailored approach, ensuring feasibility for large-scale implementation.

This structured approach will provide crucial insights into optimising individualised intervention strategies for preventing PUI in adolescents.

3. Methods

3.1. Study Setting

BootStRaP project collaborators in academic organisations across 9 European countries (France, Germany, Hungary, Lithuania, Netherlands, Portugal, Spain, Switzerland and United Kingdom) will identify several schools willing to take part. These designated schools will act as the recruitment sites for both the pilot and the RCT studies.

All data collection will be carried out via the BootstrApp and the Dragon Game app on participant's smartphones. Push notifications will guide participants through the data collection.

The sponsor is the University of Hertfordshire (UoH), an academic institution based in the United Kingdom. The study is centrally organised and based on a shared study protocol, but consent and recruitment procedures are adapted to local requirements.

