3.1.1. Description of target group

The aim of both studies is to detect early risk for problematic internet use and prevent the development of addictive usage patterns across the whole well-being spectrum, rather than to treat an already developed pathological use. The whole adolescent population is therefore included rather than specific subgroups. The study population will consist of young adolescents of all genders between 12 and 16 years, recruited from schools with different socioeconomic backgrounds and from rural and urban areas. We strive to include young people from low/middle income families who might be especially vulnerable for PUI. The BootStRaP study is designed to evaluate and moderate online behaviour among young people using mobile devices. Therefore, it is a necessary condition, that young people involved have routine and exclusive access to a mobile device to be able to take part in the study.

The eligibility criteria are:

- Age between 12 and 16 years
- Routine access to a mobile device
- Student at a school involved in the study

The exclusion criteria are:

- No exclusive access to a mobile phone
- Phone operating systems older than 15.6 for iOS or 10 for Android

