3.4. Study Participants

3.4.1. Approaching study participants

Local research teams have established links with schools involved in the earlier assessment study and have secured interest for participation in the pilot and RCT. Student ambassadors (see Section 9) contributed to the development of study materials and both the assessment and intervention apps. Within participating schools, selected classes are invited to join the study. Parents are informed in advance and asked to provide consent (see Section 4.3). During school hours, local researchers and BootStRaP Ambassadors (teachers or students) introduce the study, answer questions, and obtain student assent. Participation is entirely voluntary, with no pressure from schools.

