4.2. Recruitment

Each of the nine participating countries has established partnerships with local schools previously involved in the assessment app study, with agreements to continue in the BootStRaP project. At each school, at least one teacher and one student serve as BootStRaP Ambassadors, supporting engagement and retention throughout the pilot and RCT phases. Additional schools will be recruited if needed.

Where available, student organisations will also be engaged to support recruitment. Locally appropriate incentives (e.g. lotteries, competitions, or honoraria) will be used to encourage participation, tailored to each centre's context.

Local researchers and BootStRaP Ambassadors will introduce the study to students, explain its purpose, and demonstrate the BootstrApp Intervention app and Dragon Game app, which will be installed on students' smartphones. Students will have the opportunity to ask questions during these sessions.

Parents or guardians will receive an information pack and be invited to attend at least one session to learn more and ask questions. Participation requires parental consent and student assent. A holding page on the BootstrApp will require a unique code, provided during the information session, to confirm consent, assent, and school affiliation.

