6.1. Data Collection

Both the pilot study and RCT are controlled, randomised, observer-blind, parallel group, three-arm trials.

Data will be automatically recorded via the BootstrApp Intervention app, which was specifically developed for this study. The Dragon Game app will be used alongside the BootstrApp Intervention app to conduct cognitive assessment tasks focusing on affect regulation and inhibitory executive control.

Participants will primarily interact with the BootstrApp Intervention app, which will seamlessly guide them through all data collection activities, including automatic redirection to the Dragon Game app for cognitive assessments. This streamlined approach ensures a user-friendly experience, with minimal direct interaction required beyond the initial app installation.

To maintain participant anonymity, no names or contact information will be collected within the apps. The questionnaires and cognitive paradigms will be administered in multiple languages (Dutch, English, French, German, Hungarian, Lithuanian, Portuguese, and Spanish). Where translations are not already available, instruments will undergo a rigorous translation process, including double independent translation, back-translation into English, and validation by an expert panel from the UoH with mental health research expertise.

The measured variables are aligned with the key determinants outlined in the logic model (Figure 41). Where required, permissions and licence agreements with copyright holders of the assessment instruments have been secured to ensure compliance and ethical standards.

[figure not shown]

Figure 41. The logic model of PUI (based on (Brand, 2022; Brand et al., 2019).

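### No eligibility rule or enrolment check keeps pilot participants out of the RCT, although both studies recruit from the same schools under one set of criteria

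*Protocol*

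**What the plan says.** Protocol section 3.1 states: "These designated schools will act as the recruitment sites for both the pilot and the RCT studies". Section 3.4.1 adds that local teams "have secured interest for participation in the pilot and RCT" at schools from the earlier assessment study, and section 4.2 brings in new schools only on demand: "Additional schools will be recruited if needed".

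Section 3.1.1 has a single eligibility list for the two studies. The inclusion criteria are "Age between 12 and 16 years", routine access to a mobile device, and "Student at a school involved in the study". The only exclusions are "No exclusive access to a mobile phone" and "Phone operating systems older than 15.6 for iOS or 10 for Android". Earlier participation is not mentioned.

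Sections 3.4.1, 4.2 and 4.3 describe the approach to classes, consent, assent and the issue of the access code. None includes a check for participation in the pilot.

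Section 4.5 allocates pilot participants equally to three groups, two of them active. Section 3.2 uses the same two interventions in both studies. Sections 2.1 and 6.3.2 derive the tailoring algorithm from pilot data.

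**The concern.** A student who took part in the pilot and is still within the age range at a participating school meets every RCT criterion as written. Three things are then at stake.

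- **Active versus control.** This is the first primary RCT question in section 6.3.2. Controls who had an active intervention in the pilot may already carry some of its effect, which would narrow the contrast.
- **Tailored versus random.** This is the second primary question. The RCT is meant to test an algorithm built on other people's data. Returning students who were in the pilot's development set would be allocated partly on the basis of their own earlier response.
- **Blinding.** Section 4.5 keeps participants blinded. A student who remembers the gamified modules of Appendices A and B could recognise the information-only posts of the control condition.

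This is an eligibility rule, so it belongs in the protocol.

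**Working it through.** **1. Can the same student qualify twice?** The extension follows pilot week 18, lasts at most 28 months and ends in July 2028 (section 3.3). At full length this puts pilot entry at about late 2025. RCT follow-up is at week 30 (Table 1) and the study ends on 01/09/2028 (Study Summary), so the last RCT entry is about February 2028. That is little more than two years later, so a student aged 12 or 13 in the pilot would still be within 12 to 16. These dates are inferred, because the protocol gives no RCT start date.

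**2. The protocol's own sample size.** With d = 0.3, two-sided alpha 0.05 and power 0.80, the two-sample t-test gives 176 per group (175 by the normal approximation). Then 176/0.3/0.7 = 838 per group and 3 × 838 = 2514. Section 3.4.2 is reproduced.

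**3. The contrast to examine.** Section 6.3.2 defines active versus control as both active arms pooled, 2:1. On the basis used for sample size (176 high-risk completers per arm) this is 352 v 176.

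- Standard error in d units: √(1/352 + 1/176) = 0.0923
- Power ≈ Φ(d/0.0923 − 1.96)
- With no overlap: Φ(0.30/0.0923 − 1.96) = Φ(1.29) = 90%

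**4. Overlap.** Let q be the share of RCT participants who were in the pilot, and k the share of the earlier effect that persists. Both are assumptions, since the protocol gives neither. Assume also that the active arms gain nothing extra from a second exposure. Two of the three pilot groups are active, so the pre-exposed share of RCT controls is 2q/3, and the effective difference is 0.30 × (1 − 2qk/3).

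| q | Controls pre-exposed | d, k = 1 | Power, k = 1 | d, k = 0.5 | Power, k = 0.5 |
|---|---|---|---|---|---|
| 0 | 0% | 0.30 | 90% | 0.30 | 90% |
| 10% | 6.7% | 0.28 | 86% | 0.29 | 88% |
| 25% | 16.7% | 0.25 | 77% | 0.275 | 85% |
| 50% | 33.3% | 0.20 | 58% | 0.25 | 77% |

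With k = 0 and an unchanged response to the intervention, there is no dilution.

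**5. If all completers are analysed.** Section 6.3.2 does not restrict the primary analysis to high-risk students. Completers per arm are 838 × 0.7 ≈ 586, giving 1,172 v 586. The standard error is √(1/1172 + 1/586) = 0.0506. Even at d = 0.20, power is Φ(0.20/0.0506 − 1.96) = Φ(1.99), about 98%.

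**6. Training cases in the tailored arm.** Section 6.3.2 holds out one third of each pilot arm for validation; section 3.4.2 describes one group in four. So 2/3 to 3/4 of returning students would be training cases. Out of 838 in the tailored arm, that is 56 to 63 at q = 10%, 140 to 157 at 25%, and 279 to 314 at 50%.

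None of these calculations allows for clustering.

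**The case against.** The strongest reply is that separate samples look intended. The protocol speaks of Cohort 2 and Cohort 3, gives each its own 3,600 participants and its own randomisation, invites selected classes, and foresees additional schools. That stands as evidence of intent, but none of it is a rule against re-enrolment. Randomisation would also balance earlier exposure between RCT arms on average. That protects against baseline imbalance, but not against dilution or the reuse of training cases.

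Four stronger readings are tempting, and the documents do not support them.

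- **That the algorithm will be tested on its own training cases.** Overlap is only possible, and part of the pilot is held out for validation.
- **That overlap favours tailoring.** In the RCT, returning students would have a new baseline, a new randomisation and a newly measured outcome. Fitting noise in a pilot outcome does not predict noise in a later one, and earlier exposure could equally blunt a tailored benefit.
- **That power falls from 80% to 75%, 65% or 47%.** Those figures come from 176 v 176, which is not the 2:1 contrast that section 6.3.2 defines.
- **That overlap could never be traced.** Section 6.1 says "no names or contact information will be collected within the apps", and section 11 stores named forms separately. But section 4.3 attaches the access code to the consent and assent forms, so a route exists. What is missing is any described use of it across cohorts.

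**Conclusion.** The gap is real: applied as written, the criteria admit pilot participants to the RCT, and no enrolment step would detect them. If overlap occurs, dilution of active versus control is probable, loss of blinding is possible, and the RCT is no longer a fully independent test of the algorithm. The size cannot be known from the protocol. The fall from 90% to 86%, 77% or 58% rests on assumed overlap of 10%, 25% or 50%, full persistence of a four-week intervention's effect, no extra gain in the active arms, analysis of high-risk completers only, and no clustering. Relaxing the persistence assumption or analysing all completers shrinks the loss, in the latter case almost to nothing. The case for acting therefore rests on how easily the threat can be avoided at enrolment, and not on a demonstrated loss of power.

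**What to change.** Add to section 3.1.1, for the RCT only, an exclusion for anyone enrolled in Cohort 2 or its extension. Apply it at the step in section 4.3 where the research team verifies consent and assent and issues the access code, by checking the Cohort 2 consent list.

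Where a site cannot apply the exclusion, record Cohort 2 participation at RCT entry and repeat the primary analyses without those participants.

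The cost is one criterion and one check at a step staff already perform. The sample size of 838 per group and 2514 in total is unchanged. The downside is a somewhat narrower recruitment pool in schools that took part in the pilot, which the provision for additional schools in section 4.2 can offset.
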